3.4.2 Doses and treatment regimens

Dose

Eligible patients will be randomised 1:1 to the following treatment groups:

- Fulvestrant 500 mg given as two 5 ml intramuscular injections, one in each buttock, on days 0, 14, 28 and every 28 (\pm 3) days thereafter.

- Fulvestrant 250 mg given as two 5 ml intramuscular injections (1 Fulvestrant injection + 1 placebo injection), one in each buttock, on days 0, 14 (2 placebo injections only), 28 and every 28 (\pm 3) days thereafter.

After the database lock for the primary analysis, in line with the IDMC advice, patients will have their treatment unblinded and transferred to open label supplies. Patients who are currently receiving fulvestrant 250 mg will be given the option transfer to fulvestrant 500 mg.

After study treatment is unblinded, any patient not wishing to transfer to fulvestrant 500 mg, who remains on fulvestrant 250 mg, will receive only one 5 ml intramuscular injection, as the placebo injection previously required to preserve the double blind nature of the study is no longer needed

Route

All patients will receive two 5ml injections containing either fulvestrant or matching placebo, one into each buttock, on days 0, 14, 28, and every 28 (\pm 3) days thereafter.

Each injection will be administered into the gluteus maximus muscle using an aseptic parenteral technique, and must be administered slowly over approximately 1-2 minutes. Following administration, the injection site(s) should be assessed by the investigator for any local reaction. The patient should be instructed to report complications to the investigator. Appropriate measures such as the application of heat or cold should be instituted according to basic nursing intervention and institutional policy and pressure should be applied where appropriate – see Section 3.7. Any severe local site reaction should be treated with appropriate medical intervention.

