3.5 Method of assigning patients to treatment groups

As patients are screened for the study after signing and dating the written Informed Consent they must be allocated a 7-digit enrolment code (E-code) with the prefix 'E'.

The first four digits in the enrolment code will indicate the centre, and digits 5-7 the enrolment order for the centre (e.g., the first patient screened in centre number 0125 would be assigned the E-code E0125001, the second patient screened would be E0125002 and so on).

This number is the patient's unique identifier and is used to identify the patient on the CRFs. Enrolment numbers should be given in consecutive order. **All screened patients are assigned an E-code irrespective of whether or not they are subsequently randomised to receive study treatment.**

Patients fulfilling the eligibility criteria will be randomised into the study and assigned a randomisation code (patient number). Randomisation codes should be allocated strictly sequentially and each patient pack will be labelled with a randomisation code.

If a patient discontinues from the study, the randomisation code (patient number) will not be reused, and the patient will not be allowed to re-enter the study.

If a randomisation code is assigned incorrectly, no attempt should be made to remedy the error once study material has been dispensed. The patient will continue with the allocated randomised code and study material. AstraZeneca (or company representing AstraZeneca) should be notified as soon as the error is discovered. Randomisation of subsequent patients will continue using the first unallocated randomised code in the original sequence.

The actual treatment given to individual patients will be determined by a randomisation schedule. Patients will be allocated treatment in balanced blocks. The actual treatments will be prepared and packed by Investigational Product Section, AstraZeneca into individual patient packs (See Section 3.4.3). Complete blocks of study material will be dispensed to each centre.

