6.4 Method of statistical analysis

The hypothesis being tested in this study is:

H₀: 500 mg fulvestrant is no different than 250 mg fulvestrant

H₁: 500 mg fulvestrant is different from 250 mg fulvestrant

The hypothesis testing for treatment differences will be performed for TTP, ORR, OS and CBR. The superiority of 500 mg fulvestrant will be declared if the two-sided p-value for the treatment comparison is ≤ 0.05

No formal analysis will be performed on DoR or DoCB.

The primary analysis on the primary variable of TTP will be performed using a log-rank test (equivalent to the Cox's proportional hazards regression model with treatment factor only) in ITT population.

In addition to the log rank test for TTP (unadjusted model with treatment factor only) a Cox's regression model will also be performed with factors fitted for treatment and other baseline covariates (adjusted model).

The conclusions will be based on the unadjusted log rank test analysis as this is considered as the primary analysis. If the unadjusted analysis and the adjusted analysis yield different results, the consequence of covariate adjustment will be explored.

A secondary Per Protocol analysis of TTP will be performed using a log-rank test in order to assess the reliability of the conclusions from the primary ITT analysis.

For objective response rate and clinical benefit rate, a logistic regression model will be fitted with treatment factor only. For overall survival the log rank test will be performed (as described above for TTP). Duration of response and duration of clinical benefit will be summarised using the Kaplan-Meier method.

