6.4.1 Time to Progression

For the primary analysis of TTP, to assess efficacy of 500 mg fulvestrant against 250 mg fulvestrant, the following analysis will be carried out:

Formal treatment comparisons will be analysed using a log-rank test (equivalent to the Cox's proportional hazards regression model with treatment factor only) as a primary method. In addition, a secondary analysis using the Cox regression model will be performed to investigate any impact of baseline covariates. The following baseline covariates will be fitted in the Cox regression model:

- Age (≤ 65 vs >65)

- Response to last endocrine therapy received prior to fulvestrant (responsive / not responsive)
- Receptor status at diagnosis (both ER+ & PgR+ vs ER+ & PgR other)
- Visceral involvement (Yes/No)
- Last therapy received prior to fulvestrant (Aromatase Inhibitor (AI)/ Anti-Oestrogen(AO))
- Measurable disease (Yes/No)

The effects of centre and treatment by centre interaction will be investigated if possible; however, it is recognised that this investigation may be limited if recruitment at most centres is low, which will cause problems with computational convergence. No analysis will be performed for individual centres or a subgroup of centres.

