6.4.3 Overall Survival

The formal treatment comparison for OS will be performed using a log rank test only after the proportion of reported deaths exceeds 50% of the total number of patients to be randomised across the 2 treatment groups (i.e., at least 360 deaths). Prior to that, survival will be summarised only and will not be subjected to inferential statistical analysis.

A further OS analysis will be performed when approximately 75% of randomised patients have died. The primary OS analysis will be a log rank test to estimate the hazard ratio of 500 mg fulvestrant to 250 mg fulvestrant together with the corresponding 95% CI and p-value. A secondary analysis will be the Cox proportional hazards regression model with treatment factor and the baseline covariates specified in Section 6.4.1.

OS will be summarised using the Kaplan-Meier method. Kaplan-Meier plots and Kaplan-Meier estimates of median time to death and percentage of patients alive at six-monthly intervals will be presented for each treatment group.

Further details will be provided in the Statistical Analysis Plan for the follow-up OS analysis

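### The deciding log-rank test is valid and correctly sized, but less efficient than the covariate-adjusted Cox model the protocol already specifies

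*Protocol*

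**What the plan says.** - **Deciding test.** Sections 6.4 and 6.4.1 make the log-rank test in the ITT population, with treatment as the only factor, the primary analysis of TTP. Section 6.4 adds: "The conclusions will be based on the unadjusted log rank test analysis as this is considered as the primary analysis".
- **Adjusted model.** Section 6.4.1 provides that "a secondary analysis using the Cox regression model will be performed to investigate any impact of baseline covariates". It names six two-level factors: age, response to last endocrine therapy, receptor status, visceral involvement, type of last therapy and measurable disease.
- **If the two disagree.** Section 6.4: "If the unadjusted analysis and the adjusted analysis yield different results, the consequence of covariate adjustment will be explored". The conclusion still rests on the unadjusted test.
- **Overall survival.** Section 6.4.3 follows the same pattern: a log-rank test is primary and a Cox model with the same covariates is secondary. It closes with "Further details will be provided in the Statistical Analysis Plan for the follow-up OS analysis".
- **Randomisation.** Section 3.5: "Patients will be allocated treatment in balanced blocks" and "Complete blocks of study material will be dispensed to each centre". The ratio is 1:1 (Section 3.4.2). No prognostic stratification factor is named.
- **Stage of the trial.** The synopsis dates the data cut-off for the primary analysis to 28 February 2009. Sections 3.1 and 7.6 refer in the past tense to the 50% survival analysis as carried out together with the primary TTP analysis.

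**The concern.** In a proportional hazards setting, leaving prognostic factors out of the analysis pulls the estimated treatment hazard ratio towards 1 and costs power, even when the arms are perfectly balanced. The usual remedies are to stratify the randomisation and the test on the main factors, or to adjust for them. This design does neither in the test that decides. Blocking by centre does little here: 720 patients over about 150 centres is 720/150 = 4.8 per centre, and balance within a centre does not balance visceral disease or prior endocrine response.

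The plan already lists plausible prognostic factors and fits them. It corrects for them only in secondary models that cannot change the decision. At stake are a few points of power at no cost in patients, in a trial sized at 80% for a 1.38-month gain in median TTP.

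**Working it through.** **1. Reproduce the plan's own figure (Section 6.5).** Inputs: HR 0.8, two-sided 5%, 80% power, 1:1.

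- Schoenfeld: events = 4(1.960 + 0.842)² / (ln 0.8)² = 4 × 7.849 / 0.0498 ≈ 631.
- Freedman: events = [(1 + 0.8)/(1 − 0.8)]² × 7.849 = 81 × 7.849 ≈ 636.
- Power at 632 events: Φ(½√632 × 0.2231 − 1.960) = Φ(0.845) = 80.1%.

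The stated 632 reproduces, for exactly the unadjusted test that is planned.

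**2. Compare the two analyses by simulation.** From Section 6.5: 720 patients 1:1, uniform accrual over 36 months, exponential TTP, control median 5.5 months, analysis at the 632nd event. From Section 6.4.1: six binary covariates. Assumed, because the protocol gives no values: independent covariates, 50% prevalence, with the hazard ratios in the first column. There were 3,000 replicates per scenario for the overall reading and 2,000 for the conditional reading; Monte Carlo error is about 1 point.

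| HR per covariate | HR 0.8 is the overall effect: log-rank / adjusted Cox | HR 0.8 is the conditional effect: log-rank / adjusted Cox |
|---|---|---|
| 1.0 (no effect) | same as next column | 80.4% / 80.0% |
| 1.2 each | 80.8% / 83.5% | 76.4% / 78.7% |
| two at 1.5, four at 1.1 | 80.6% / 85.1% | 75.1% / 79.1% |
| 1.35 each | 83.3% / 87.7% | 72.1% / 79.7% |
| 1.5 each | 80.6% / 90.3% | 66.8% / 79.7% |

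The gain is about 3 to 10 points on the overall reading and about 2 to 13 points on the conditional reading. The 83.3% entry is a little high because the mean unadjusted HR in that scenario came out at 0.795, for which the formula in step 1 gives Φ(12.570 × 0.2290 − 1.960) = 82%.

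On the conditional reading, the mean unadjusted HR is 0.807, 0.816 and 0.826 for covariate HRs of 1.2, 1.35 and 1.5, which shows the pull towards 1. A separate run of 1,500 replicates at covariate HRs of 1.2, 1.3 and 1.5 gave 77/80%, 72/79% and 67/79%.

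**3. Type I error.** With no treatment effect, simulated rejection rates were 4.6-5.0% for the log-rank and 4.1-5.4% for the adjusted Cox model. Both hold 5%.

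**4. Chance imbalance.** With 360 per arm and 50% prevalence, the standard deviation of the difference in proportions is √(0.25 × 2/360) = 0.0373, so the 95% limit is 1.96 × 0.0373 = 7.3 percentage points. The shift in log HR is 0.073 × ln(covariate HR): 0.073 × 0.182 = 0.013 for HR 1.2 and 0.073 × 0.405 = 0.030 for HR 1.5. That moves the treatment HR by about 1.3% to 3.0% per factor.

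**5. How much OS information has been seen.** Section 6.4.3 requires at least 360 deaths for the first OS analysis. The second comes at about 0.75 × 720 = 540 deaths. So at least 360/540, or two thirds, of those deaths have already been analysed by treatment arm.

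**The case against.** The strongest reply is that this is a defensible choice and not a mistake. An unadjusted log-rank test matches a randomisation without prognostic strata, holds its error rate, needs no modelling of covariates, and was the test the sample size was computed for. Section 6.4 says in advance which analysis decides. All of this stands.

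Three stronger readings are tempting, and the documents do not support them.

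- *The trial is underpowered.* A reader could infer this from the 67-77% figures. Those require 0.8 to be a covariate-conditional effect. Section 6.5 ties 0.8 to overall medians (5.5/0.8 = 6.88 months against 5.5), which points to the overall reading, where the log-rank keeps its 80%.
- *Chance imbalance is left uncorrected.* It is corrected in pre-specified secondary models for both TTP and OS, and the 5% error rate of the unadjusted test already allows for it. Only the deciding test makes no correction.
- *The remedy is a wording change that can still be made throughout.* The TTP analysis has been done, so replacing its deciding test now would be a change of primary analysis after unblinding.

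The size of the gain is also open to challenge. Six independent factors each at HR 1.5 imply a 1.5⁶ ≈ 11-fold hazard range between extreme patients. Independence is doubtful too: patients without measurable disease enter through bone lesions (Section 3.3.2), so measurable disease and visceral involvement probably overlap. This weakens the upper end of the range but not the direction.

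**Conclusion.** The point holds as an efficiency criticism of the design. The planned test is valid and delivers its stated power, but the protocol already contained a more powerful analysis and gave it no part in the decision. For TTP, adjustment would have raised power from about 80-83% to 84-90% if 0.8 is the overall effect, or from about 67-77% to 79-80% if it is the conditional effect.

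These figures rest on six balanced, independent binary covariates each with HR 1.2 to 1.5, which is an assumption. If the covariates are not prognostic, the gain is zero and nothing material is lost. The figures are for TTP at 632 events. The protocol states no power for OS, so they show only the direction of any gain there.

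**What to change.** **What the design should have fixed before unblinding.** Make the treatment effect from the Cox model with the six Section 6.4.1 covariates the deciding analysis, or use a log-rank test stratified on two or three of them. Code unknown values as their own category, and keep the unadjusted log-rank as the sensitivity analysis.

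**What to do now.**

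- *TTP:* leave the deciding test as planned.
- *75% OS analysis:* give the adjusted analysis the deciding role through the follow-up OS SAP to which Section 6.4.3 defers. That section names the log-rank as the primary OS analysis, so amend its wording or record the departure. Use the covariate list as it stands, without selection, and define the category for unknown values. State that the change was made after unblinding and on design grounds alone. Always report the planned log-rank result beside it.

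**Cost.** Wording only, with no extra patients or data. There are two real downsides. The reported hazard ratio becomes conditional on the covariates, which must be stated. And the OS change comes after the 50% results are known, so it carries less weight than one fixed in advance.

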6.4.1 Time to Progression

For the primary analysis of TTP, to assess efficacy of 500 mg fulvestrant against 250 mg fulvestrant, the following analysis will be carried out:

Formal treatment comparisons will be analysed using a log-rank test (equivalent to the Cox's proportional hazards regression model with treatment factor only) as a primary method. In addition, a secondary analysis using the Cox regression model will be performed to investigate any impact of baseline covariates. The following baseline covariates will be fitted in the Cox regression model:

- Age (≤ 65 vs >65)

- Response to last endocrine therapy received prior to fulvestrant (responsive / not responsive)
- Receptor status at diagnosis (both ER+ & PgR+ vs ER+ & PgR other)
- Visceral involvement (Yes/No)
- Last therapy received prior to fulvestrant (Aromatase Inhibitor (AI)/ Anti-Oestrogen(AO))
- Measurable disease (Yes/No)

The effects of centre and treatment by centre interaction will be investigated if possible; however, it is recognised that this investigation may be limited if recruitment at most centres is low, which will cause problems with computational convergence. No analysis will be performed for individual centres or a subgroup of centres.

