3.3.2 Inclusion criteria

For inclusion in the study, patients must fulfil all of the following criteria:

1. Provision of written informed consent
2. Histological/cytological confirmation of breast cancer
3. Documented positive oestrogen receptor status (ER +ve) of primary or metastatic tumour tissue, according to the local laboratory parameters.
4. Requiring hormonal treatment:
 - (a) Relapsing during, or within 12 months of completion of, adjuvant endocrine therapy (tamoxifen, toremifene or aromatase inhibitors such as anastrozole, letrozole and exemestane), or
 - (b) Progressing on an endocrine therapy (tamoxifen, toremifene or aromatase inhibitors such as anastrozole, letrozole and exemestane) provided that this endocrine treatment was started at least 12 months after the completion of adjuvant endocrine treatment, or
 - (c) Progressing on an endocrine therapy (tamoxifen, toremifene or aromatase inhibitors such as anastrozole, letrozole and exemestane) given as first treatment for patients with *de novo* advanced* breast cancer

* Advanced breast cancer: Metastatic disease or locally advanced disease which is not amenable to treatment with curative intent.

5. Patients fulfilling one of the following criteria:
 - Patients with measurable disease as per RECIST criteria. This is defined as at least one lesion that can be accurately measured in at least one dimension (longest diameter to be recorded) as ≥ 20 mm with conventional techniques or as ≥ 10 mm with spiral CT scan.
 - Patients with bone lesions, lytic or mixed (lytic + sclerotic), in the absence of measurable disease as defined by RECIST criteria
6. Postmenopausal woman, defined as a woman fulfilling any 1 of the following criteria:
 - Age ≥ 60 years.
 - Age ≥ 45 years with amenorrhoea ≥ 12 months with an intact uterus.
 - Having undergone a bilateral oophorectomy.

- FSH and oestradiol levels in postmenopausal range (utilising ranges from the local laboratory facility).
 - In patients who have previously been treated with an LH-RH analogue, the last depot must have been administered more than 4 months prior to randomisation, menses must not have restarted, and FSH and oestradiol levels must also be in the postmenopausal range (utilising ranges from the local laboratory facility).
7. WHO performance status 0, 1 or 2.

For inclusion in the translational research component of the study, patients must fulfil the following criteria:

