6.4.5 Quality of life

The FACT-B quality of life instrument is to be used for this trial and the number of patients required for the analysis is based on the trial outcome index (TOI) within the FACT-B. This measure is the sum of the functional well being, physical well being and breast cancer subscale dimensions of the questionnaire.

Analyses on QoL data will be carried out using the ITT population as primary and will also be performed by study treatment actually received (i.e. patients who received at least one dose of the medication to which they were randomised) as supportive.

All FACT-B items will be scored such that a higher score represents a better QoL.

The TOI, total FACT-B and the FACT-G will be analysed longitudinally using a model with baseline covariates (as detailed in Section 6.4.1) to examine the difference in the TOI between the fulvestrant 500mg and fulvestrant 250mg groups.

The above QoL endpoints for each treatment group at each time point will be summarised using descriptive statistics and will also be presented graphically.

Also, an analysis of the time to deterioration in QOL will be carried out in the same way as the analysis of time to progression. QOL information will be collected at 4, 8, 12, 16, 20 and 24 weeks and this discrete data collection will be accounted for in the analysis by replacing the proportional hazard model with the discrete logistic model (by using the TIES = DISCRETE option in the MODEL statement of PHREG in SAS). For an individual patient a deterioration in QOL is defined as a decrease in TOI from baseline of 5 points or more. If a subject has not shown a reduction of 5 points or more at the time of analysis then the observation will be right censored using the last QOL assessment date. Covariates will be included as above.

Missing data handling for the TOI and FACT-B scales:

The reason for missing data will be identified. If data is missing at random, the technique outlined below will be used. If there is any evidence that the missing data is systematic, missing values will be handled to ensure that any possible bias is minimised. If there are

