6.5 Determination of sample size

The sample size calculation is based on the primary variable, TTP, and assumes exponential survival times. The sample size is driven by the number of required events. In order to detect a hazard ratio of ≤ 0.8 (or ≥ 1.25) for 500 mg fulvestrant compared to 250 mg fulvestrant, at a 2-sided significance level of 5%, with 80% power, approximately 632 events are required to have occurred in the study (i.e., 632 patients to have progressed or died)

The median time to progression for 250 mg fulvestrant in this patient population is estimated to be 5.5 months (Robertson et al 2003). A hazard ratio of 0.8 would equate to a prolongation in median TTP for 500 mg fulvestrant over 250 mg fulvestrant of 1.38 months (i.e., a median TTP of 6.88 months for 500 mg fulvestrant compared to median TTP of 5.5 months for 250 mg fulvestrant).

If 720 patients are recruited over a period of 36 months, it is anticipated that the required 632 events would be observed approximately 6 months following the end of recruitment.

The initial survival analysis will be performed after the proportion of reported deaths exceeds 50% of the total number of patients required. If 50% of deaths occur before the 632 progression events then the survival analysis will not be carried out until the 632 progression events are observed and the data is unblinded for the TTP analysis. A further overall survival analysis will be performed when approximately 75% of randomised patients have died.

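### Minor: the covariate list shared by the adjusted TTP, OS and QoL models leaves out WHO performance status, although it is recorded at baseline for every eligible patient

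*Protocol*

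**What the plan says.** Section 6.4.1 introduces the adjusted TTP model with "The following baseline covariates will be fitted in the Cox regression model" and lists six items: age, response to last endocrine therapy, receptor status, visceral involvement, type of last therapy and measurable disease.

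The list is then reused:
- OS, section 6.4.3: "A secondary analysis will be the Cox proportional hazards regression model with treatment factor and the baseline covariates specified in Section 6.4.1".
- QoL, section 6.4.5: TOI, FACT-B and FACT-G are "analysed longitudinally using a model with baseline covariates (as detailed in Section 6.4.1"). The time-to-deterioration analysis takes the same covariates.

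Performance status appears elsewhere. Section 3.3.2 requires "WHO performance status 0, 1 or 2", section 4.2 includes it in the screening data, and Table 1 schedules it at screening and Visit 1. Section 3.5 describes allocation in balanced blocks, with complete blocks sent to each centre, and names no prognostic stratification factor.

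Section 6.4 rests the TTP conclusion on the unadjusted log-rank test, and section 6.4.3 makes the log-rank test primary for OS. Sections 3.1 and 7.6 report that the TTP and 50% survival analyses have been performed. The analysis at about 75% deaths is still to come, and section 6.4.3 promises a separate SAP for it.

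**The concern.** If the adjusted and unadjusted TTP results differ, section 6.4 says the effect of the adjustment will be explored. The adjusted models are therefore where a chance imbalance between the arms would show. A baseline variable that every eligible patient has, and that the described randomisation does not balance, is an obvious candidate for them. If performance status predicts survival, a model without it loses some precision and cannot correct for an imbalance in it.

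The OS model matters most because it can still be changed before its data are cut. At stake is the quality of a supportive estimate, not the trial's conclusion.

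**Working it through.** **Inputs from the protocol.** 720 patients randomised 1:1 and 632 TTP events (section 6.5); "In order to detect a hazard ratio of ≤ 0.8 (or ≥ 1.25"), "at a 2-sided significance level of 5%, with 80% power"; control median 5.5 months; a further OS analysis at about 75% deaths.

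**Assumptions, because the protocol gives no figures.** Performance status 0/1/2 in 50/40/10% of patients; hazard ratio per level between 1.2 and 2.0; treatment hazard ratio 0.80 within each level. For OS, 0.80 is borrowed from the TTP design.

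**1. The plan's own figure.** Schoenfeld events = 4 × (1.960 + 0.842)² / (ln 0.8)² = 631 after rounding up. Freedman's formula gives 636. The stated 632 is reproduced, and power at 632 events is 80.1%. The median also agrees: 5.5 / 0.8 = 6.875 months. No covariate enters this calculation, so changing the list cannot move it.

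**2. OS reference point.** Deaths = 0.75 × 720 = 540. Power at hazard ratio 0.80 = Φ(√540/2 × 0.2231 − 1.960) = Φ(0.633), about 74%. A model that includes performance status should come close to this.

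**3. OS power with and without performance status.** Simulation of 720 patients with exponential times and a cut at 75% deaths, 5,000 trials per row. The two models are treatment only and treatment plus performance status.

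| Hazard ratio per level | Without | With | Gain (points) |
|---|---|---|---|
| 1.3 | 72.5% | 73.3% | 1 |
| 1.5 | 70.0% | 72.7% | 3 |
| 1.8 | 65.6% | 72.9% | 7 |
| 2.0 | 64.4% | 73.2% | 9 |

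**4. The same comparison for TTP at 632 events.** At 1.2 and 1.4 per level, power rises from 78.4 to 79.3% and from 76.9 to 80.0%. A separate set of 400 trials per value (Monte Carlo error about 2 points) covers 1.3, 1.6 and 2.0 per level. Power there is 84, 79 and 71% without performance status, against 85, 83 and 80% with it. The average treatment hazard ratio is 0.800, 0.807 and 0.822 without it, against 0.797, 0.794 and 0.800 with it. Omission thus pulls the estimate towards 1.

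**5. Chance imbalance.** If half the patients have status 1 or 2, the between-arm difference in that share has SD √(0.25 × 4/720) = 0.037. It exceeds 1.96 × 0.037 = 0.073, or 7.3 percentage points, in about 1 trial in 20. Treating this as a one-level shift, the log hazard ratio moves by 0.073 × ln 1.5 = 0.030 at a hazard ratio of 1.5 per level, and by 0.073 × ln 2.0 = 0.051 at 2.0. The standard error at 540 deaths is 2/√540 = 0.086. An imbalance of that size therefore moves the estimate by about 0.3 to 0.6 of a standard error, in either direction.

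**The case against.** **Covariate choice is a judgement.** The protocol pre-specifies six factors and nowhere says that performance status is prognostic. This stands: the omission is not an error, and every prognostic strength used above is assumed.

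**The simulation does not test the planned model.** It compares performance status with no covariates, not with the six listed. This also stands. Any overlap with age, visceral involvement or the other factors would shrink the gain. The simulation also fits performance status as three ordered levels, whereas a 0 vs 1-2 split recovers somewhat less. The 9-point gain needs a hazard ratio of 2.0 per level, which is fourfold between status 0 and 2.

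**The timing is late.** The TTP and 50% survival results are in, so rewriting section 6.4.1 now would alter models after their results are known. This stands for TTP and the 50% OS analysis, and for any QoL model already run. The QoL models also rest on only about 100 patients, so an extra parameter costs more there. It does not rule out a dated change to the 75% OS model before its data cut.

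**A stronger reading that a reader might infer.** The list includes "Response to last endocrine therapy received prior to fulvestrant (responsive / not responsive"), and section 3.3.2 admits patients "Relapsing during, or within 12 months of completion of, adjuvant endocrine therapy". One could conclude that these patients have no value for the factor, drop out of the adjusted models and cost them much of their power. The protocol does not support this. It says neither that these patients are unclassified nor that they are excluded, and it gives no expected share of them. It leaves the term undefined, and how to class adjuvant relapses is a definition that the SAP can supply. Any power loss computed from this reading would rest on an invented share and an assumed deletion of patients.

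**Conclusion.** The point holds as a minor one. Performance status is available at baseline, the described randomisation does not balance it, and every model that uses the section 6.4.1 list omits it. The TTP and OS conclusions are unaffected because they rest on unadjusted log-rank tests.

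The benefit is some precision and some protection against chance imbalance in a supportive OS analysis. If performance status is only weakly prognostic, the benefit is negligible. A reader should not infer that the omission favours the 500 mg arm: in the simulations it moved the hazard ratio towards 1, and a chance imbalance could go either way.

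**What to change.** Before the data cut for the 75% survival analysis, add WHO performance status (0 vs 1-2) to the secondary adjusted OS Cox model in section 6.4.3 and in the SAP for that analysis. Report the model with the six listed covariates alongside, so that the two survival analyses stay comparable. If performance status is added to the completed TTP or 50% OS models, or to QoL models already run, label the result a sensitivity analysis. Leave the log-rank tests, event target and sample size as they are.

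The cost is one parameter against about 540 deaths and no new data collection. The drawback is an adjusted OS model that differs from the one specified at the 50% analysis, which reporting both models makes visible.
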